Participants who are interested and preliminarily appear eligible for this study will be invited to sign up for an information session (specific to this study), at which prospective participants learn more detailed information about the study and the enrollment process (including risks, benefits, and alternatives to participation) and have the opportunity to ask additional questions. Finally, participants who remain interested are scheduled for a remote study visit, when research staff will complete assessment of other aspects of eligibility that were not well suited for the phone screen (e.g., measurement of weight, psychiatric conditions). Participants that completed all materials at the time of the study visit will be sent a copy of the study consent to review. After the clinic visit, index participants will be randomized to treatment condition, stratifying by biological sex and baseline BMI category. During Session 0, participants will review the study consent form with a member of the research team present, able to answer any questions the participant may have. After eligibility is determined and all enrollment requirements are complete, the participant will digitally sign the consent form.

During enrollment, all index participants will nominate one friend or family member to provide support for their LM efforts. After a friend/family member has been selected, the friend/family member will be sent an email from study staff. The email will give a description of the study and provide the friend/family member a link to complete an online consent form and complete self-report measures. The friend/family member will be given the opportunity to sign up for a visit with study staff if they have additional questions. After providing consent, the friend or family member will be asked to participate in one webinar at the start of the program and three booster zoom meetings (at Months 6, 12, and 18) to learn how to provide support for the participant's LM efforts.

b) Inclusion and Exclusion Criteria

Overweight/obese index participants (N = 320) will be recruited and screened by website to assess initial eligibility.

Inclusion criteria for index participants:

- Individuals must be of overweight or obese BMI (27-50 kg/m²)
- Individuals must be adults (aged 18-70)
- Able to engage in physical activity (defined as walking two city blocks without stopping)

- Access and willingness to use a smartphone and internet

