All index participants will receive a 24-month lifestyle modification (LM) intervention. They will receive 20 sessions of group-based behavioral treatment for weight loss. Groups will meet weekly in months 1-3 over the Zoom videoconferencing platform. In months 4-24, one group meeting held over Zoom will take place every 3 months, and two brief (15-minute) individual coach phone calls will occur twice per quarter (14 calls in total over 21 months). During phone calls, coaches will check in about progress towards goals, review core behavioral skills that are most relevant, and collaboratively set goals for the next month. All index participants also will regularly exchange program text messages with the LM coach; with fellow LM participants; and with a designated friend/family member. All index participants will be instructed to use digital self-monitoring devices daily (PA sensor, food record app, smart scale) throughout the program.

Treatment Conditions

The content of the text messages (in particular, whether or not the message includes the participant's digital device data) delivered during months 4-24 will vary according to treatment condition. These three treatment conditions will be provided to 50% of participants, with an equal number of participants randomized to have each of the below three treatment conditions ON or OFF. For example, 160 index participants will have their self-monitoring digital data accessible to their friend/family member, and 160 participants will not have this feature as part of their intervention. Random assignment will be conducted using minimization procedures, which results in better condition balance than simple randomization. Baseline covariates used for randomization will include biological sex and BMI.

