
Statistical Analysis

Descriptive statistics and exploratory graphing will be generated for all variables. Data summaries will be produced for the full sample and by condition. Continuous variables will be transformed if necessary. Baseline characteristics will be compared for each ON versus OFF contrast, as well as for each of the 8 study arms, using ANOVAs for continuous variables and a chi-square tests for categorical variables. Key baseline variables that differ by condition will be considered for use as covariates in the analyses described below. Likelihood-based estimation methods and multiple imputation models

will be used to handle missing data.

Aim 1

This study will evaluate the hypotheses that long-term weight loss (primary outcome) and PA and calorie intake (secondary outcomes) will be superior in Coach Share ON vs. OFF; in Group Share ON vs. OFF; and in Friend/Family Share ON vs. OFF. We will model the pattern of change in weight over time using multilevel models. The first level will model individual weight loss over time with baseline as time 0. At the second level, the individual intercept and slope will be entered as outcomes with each of the three types of data sharing examined separately as a predictor. The cross-level interaction between time and type of data sharing (e.g., Coach Share ON vs. OFF) will be used to determine the effect of the partnership factor on the pattern of change in weight. Restricted maximum likelihood will be used to estimate model parameters and to test the significance of random effects. Both linear and higher-order time effects will be examined. Similar multilevel models will separately examine the effect of each of the three partnerships on PA and calorie intake. As an exploratory aim, we also will test the interaction effects of the three data sharing partnerships by adding higher-order interaction terms to the aforementioned multilevel models.

Aim 2

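### Covariates are picked by tested baseline imbalance, which will almost never select the allocation variables (sex, BMI), and the Aim 1 wording leaves unclear whether the three factors share one model

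*Protocol*

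**What the plan says.** **Covariates.** The Statistical Analysis section of the protocol compares baseline characteristics by ANOVA or chi-square test for each of the three ON/OFF contrasts and across the eight arms. It then says: "Key baseline variables that differ by condition will be considered for use as covariates in the analyses described below". It gives no significance threshold, and it states no other covariate rule for the Aim 1 models.

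**Allocation.** Treatment Conditions (section 11g) says: "Random assignment will be conducted using minimization procedures, which results in better condition balance than simple randomization". It adds: "Baseline covariates used for randomization will include biological sex and BMI". Recruitment Methods (section 11a) says "index participants will be randomized to treatment condition, stratifying by biological sex and baseline BMI category". The analysis section does not carry either variable into the Aim 1 models.

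**Factors in the model.** Under Aim 1, the individual intercept and slope are the level-2 outcomes, "with each of the three types of data sharing examined separately as a predictor". The test of each factor rests on this term: "The cross-level interaction between time and type of data sharing". For the secondary outcomes, "Similar multilevel models will separately examine the effect of each of the three partnerships on PA and calorie intake". The exploratory interactions are tested by "adding higher-order interaction terms to the aforementioned multilevel models".

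**The concern.** Minimization forces the arms to be alike on sex and BMI. A covariate rule triggered by a difference between arms will therefore pass over these two variables and pick up others that differ by chance. Yet an analysis should normally carry the allocation variables. If they predict the outcome and are left out, the reported standard error still contains variation that minimization has already removed from the comparison, so the test is too conservative.

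The model wording raises a second problem. It can mean three terms in one model or three one-factor models. Under the second reading, the other two randomized factors stay in the error term. A product term added to a one-factor model would also lack one of its main effects. Aim 1 explicitly asks whether effects are additive, antagonistic or synergistic, and Aim 3 builds on the Aim 1 model, so both inherit the ambiguity.

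**Working it through.** **Inputs from the protocol.** N = 238 for 80% power at 0.05; 320 enrolled with up to 25% attrition; four assessment points; ratio of level-1 coefficient variability to residual variability of at least one; 160 ON and 160 OFF per factor.

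**The plan's own figure.** 320 x 0.75 = 240, which covers 238, so the attrition allowance is consistent. The 238 itself cannot be reproduced because no effect size is stated. Back-solved for a two-sided, two-group comparison: d = (1.960 + 0.842) x 2/sqrt(238) = 0.363 SD.

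**What the rule selects.** Minimized trials of 320 over eight arms were simulated, with an assumed 0.05 cut-off, biased-coin probability of 0.6 to 1.0, and two to four BMI categories (1,500 trials per scenario). Sex was never flagged by any of the four tests. BMI was flagged in at most 0.67% of trials. Under simple randomization each would be flagged in 16% to 17% of trials, and a variable unrelated to the allocation is flagged about as often (17%). This shows what the rule picks; it is not a harm in itself.

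**Cost of omitting sex and BMI.** Let r be the share of estimated-slope variance that they explain (assumed; the protocol gives none). With 240 completers:

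- Reported SE = 2/sqrt(240) = 0.1291; true SE = 0.1291 x sqrt(1 - r)
- Type I error = 2(1 - Phi(1.96/sqrt(1 - r)))
- Unadjusted power = Phi((0.363 - 1.96 x 0.1291)/true SE)
- Adjusted power = Phi(0.363/true SE - 1.96)

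| r | Type I error, unadjusted | Power, unadjusted | Power, adjusted | Loss (points) |
|---|---|---|---|---|
| 1% | 4.9% | 80.5% | 80.7% | 0.3 |
| 2% | 4.8% | 80.6% | 81.1% | 0.5 |
| 5% | 4.4% | 80.9% | 82.3% | 1.4 |
| 10% | 3.9% | 81.6% | 84.3% | 2.7 |
| 15% | 3.4% | 82.3% | 86.3% | 4.0 |

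If the shares refer to true slopes, take the protocol's ratio of one and four equally spaced points (spacing assumed). At times 0 to 3, Sxx = 2.25 + 0.25 + 0.25 + 2.25 = 5, and slope reliability is 1/(1 + 1/5) = 0.833. The five shares become r = 0.8, 1.7, 4.2, 8.3 and 12.5%, and the losses 0.2, 0.5, 1.1, 2.3 and 3.3 points.

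A simulation of minimized four-visit trials (6,000 per row, N = 240) agrees. With a level effect only, type I error was 4.9% and there was no loss. At a 15% true-slope share, type I error was 3.4% and power was 81.9% unadjusted against 85.0% adjusted.

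**Form of adjustment.** In REML mixed models at a 10% share, adding sex and BMI as level terms only left the factor-by-time SE unchanged (ratio 1.000). Adding their time interactions as well gave 0.955. The gain comes entirely from the time interactions.

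**One-factor models, main effects.** Omitting two balanced factors of b SD each raises residual variance to 1 + 2 x b^2/4. At b = 0.2 this is 1.02, and power falls from 80.3% to 79.6% or 79.8%, depending on whether the omitted factors are taken to widen the sampling error or only the reported SE. That is a cost of 0.5 to 0.8 points. At b = 0 the cost is zero.

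**One-factor model plus a product.** Take a 0/1-coded Coach x Group product added to a Coach-only model, with no true interaction. Its coefficient then estimates Group's effect b among the 120 participants with Coach ON, with SE = sqrt((1 + b^2/8) x 4/120).

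| Group effect b (SD) | Rejection by formula | Simulated (6,000 each) | Simulated, all lower-order terms kept |
|---|---|---|---|
| 0.1 | 8.5% | 8.3% | 4.8% |
| 0.2 | 19.4% | 20.0% | 4.8% |
| 0.363 | 50.5% | 49.6% | 5.1% |

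At b = 0 the formula gives the nominal 5%. With effect coding and Group's main effect still omitted, the simulated rate was 4.7% to 4.8%.

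**The case against.** The strongest reply is that nothing here is an error in the main tests. Estimates are unbiased, false positives are not inflated, and unadjusted power stays at or above 80% for every r in the table, because minimization already helps the unadjusted test. The loss is relative to a better analysis and rests on assumed shares. Adding the covariates in the usual way, without time interactions, gains nothing. All of this stands and limits the size of the point.

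The covariate sentence is also permissive: variables are only to be considered, with no cut-off and no bar on sex or BMI. That is true. But it states a rule and ties it to named tests, so this is not detail left to an analysis plan; and it leaves covariate choice until after the baseline data have been seen.

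The 19% and 50% false-synergy figures need several things at once: one-factor models, 0/1 coding, an omitted main effect and a real Group effect. The protocol states neither the coding nor the omission. Adding higher-order terms most naturally presupposes all factors in one model, and the analysis is exploratory. This also stands: the figures show what the looser reading permits, not what the protocol prescribes. The difficulty is that the repeated emphasis on separate examination points the other way, and the text does not settle it.

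The difference between BMI and BMI category, and between stratifying and minimization, is clerical. No result above depends on it.

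**Conclusion.** The point holds as a free improvement. The covariate rule is disconnected from the allocation method and will almost never select sex or BMI. The cost is between nothing (level effects only) and about 4 power points (15% of estimated-slope variance), assuming an effect of 0.363 SD, 240 completers and a two-sided 0.05 test. It does not by itself take power below 80%.

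The model wording is ambiguous. For main effects, the one-factor reading costs at most 0.8 points if the other factors have effects of up to 0.2 SD. For the exploratory interactions, combined with 0/1 coding, it could present a genuine Group effect as synergy.

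**What to change.** For each outcome, prespecify one multilevel model that contains:

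- all three factors, effect-coded -0.5/+0.5, with their time interactions;
- biological sex and baseline BMI, in the form used for allocation, with their time interactions, whatever the baseline comparisons show.

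For the exploratory analysis, add the two- and three-way factor products and their time interactions to that same model and keep every lower-order term. Replace the wording about separate examination with a statement that the three factors are entered together. Report baseline comparisons descriptively and delete test-based covariate selection. While editing, describe the allocation method and the form of BMI in the same terms in Recruitment Methods and Treatment Conditions.

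The cost is analysis wording only. Sex and BMI are already collected for allocation, so no new data, visits or participants are needed.

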Adults attempting weight loss through lifestyle modification (LM) typically find maintenance of behavior change difficult. Outcomes might be improved if participants are provided with sustained sources of accountability and support and ongoing opportunities to reflect with others on goal progress. This study proposes that sharing digital data with other parties has the potential to improve long-term weight loss. The proposed study will enroll adults (“index participants”) (N = 320) with overweight/obesity in a 24-month LM program and instruct them to use digital tools for self-monitoring of weight, physical activity, and eating on a daily basis. Groups will meet remotely each week in months 1-3 to initiate weight loss. In months 4-24, intervention contact will be remote and will include the following: quarterly group meetings held via videoconference; brief phone calls with the coach held twice per quarter; and monthly text messages with the coach, with a small group of fellow group participants, and with a friend or family member outside of the program. Text message content will vary according to treatment condition, i.e. three types of data sharing partnerships: Coach Share, Group Share, and Friend/Family Share. Outcomes will be measured at months 0, 3, 6, 12, and 24. Primary aims include determining if Coach Share, Group Share, and Friend/ Family Share each improve long-term weight loss, PA, and calorie intake, and examining if effects are additive when participants are assigned to engage in more than one type of data sharing partnership. The secondary aim is to explore mediators and moderators of intervention effects. The tertiary aim is to determine how the quality of relationship with coach, group members, and friends/family member over time may differentially moderate treatment effects and predict data sharing efficacy. As digital technology makes data sharing increasingly feasible, it is critical to determine how to optimize these partnerships to improve long-term outcomes in LM.

2) Protocol Title

Sharing Digital Self-Monitoring Data with Others to Enhance Long-Term Weight Loss: A Randomized Trial using a Factorial Design

3) Sponsor / Funding

National Institutes of Health

4) IRB Review History

This is an original IRB submission for this project.

5) Investigator

[name], Principal Investigator
Drexel University

[name], Co-Investigator
Drexel University

[name], Co-Investigator
Rowan University

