- 1) Coach Share: The behavioral coach will view digital self-monitoring data throughout the program and will directly address data observations during intervention contacts.
- 2) Group Share: Participants in a given LM group will view each other's self-monitoring data in their small-group text messages.
- 3) Friend/Family Share: A friend or family member will view the participant's data via automated text message.

Coaches, group members, and friends/family in Share conditions will be trained to respond to shared data in ways that support motivation and self-regulation, without judgment or a critical tone. With the 2 x 2 x 2 factorial design, index participants will be randomly assigned such that half receive Coach Share and half do not; half receive Group Share and half do not; and half receive Friend/Family Share and half do not. Amount of intervention contact between the participant and each party is comparable in all conditions, isolating the effects of data sharing. Outcomes will be measured at months 0, 3, 6, 12, and 24.

8) Setting of the Human Research

Group treatment for all months will be held over Zoom videoconferencing software. All study visits will be held remotely and copies of physical data will be held at Drexel's University City Campus.

9) Resources Available to Conduct the Human Research

Center for Weight, Eating and Lifestyle Science (WELL Center)

Drexel University's WELL Center is actively engaged in vibrant research initiatives to advance the science and practice of weight control. The WELL Center currently houses 26 faculty, staff, and trainees and has a portfolio of \$15M in research funding. Adequate space in the WELL Center will be devoted to this project. Project staff will have offices available for conducting project management tasks, conducting phone screening of participants, conducting assessments, and storing data and project supplies. The WELL Center is primarily a research center, but there is also an arm with a clinic that serves the community. There is no involvement of the clinic in this study.

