[name] and [name], principal and co-investigator on the project respectively, are experts in the area of the development of treatments for health-related behavior change. Their lab has several NIH-funded research grants related to eating behavior and lifestyle modification, many of which [name] (co-investigator) similarly has the primary responsibility of data analyses. [name] (co-investigator) is an expert in the areas of community nutrition science and cancer prevention. [name] (co-investigator) specializes in understanding social influences on health and health behavior (e.g., social comparison, social support) and harnessing social influences to improve outcomes in health behavior interventions (e.g., for weight loss and physical activity promotion). [name] (co-investigator) has more than 30 years of experience leading interdisciplinary science teams funded by NIH, VA, and foundation grants to develop and evaluate technology-supported interventions that promote healthy change in multiple chronic

disease risk behaviors, particularly poor quality diet, physical inactivity, obesity, and smoking.

Collective research expertise from the team and past success recruiting for studies ensure that this study will likewise be successful in its recruitment goals. As described in Recruitment Methods below, 320 index participants will be recruited in five cohorts (n = 64 per cohort) through digital media, radio stations, and public transportation, and publicizing the program in primary care practices and community centers. These methods have yielded large samples in previous NIH-funded clinical trials conducted at the WELL Center by this research team. Also, to enhance retention, study staff will send newsletters and birthday/holiday cards to participants. All study staff are well-qualified and well-trained in conducting weight and eating-related research, as well as general best practices for research with human subjects. All persons assisting with research will be trained and monitored by the Principal Investigator.

Department of Psychology

The Department of Psychology is actively engaged in research initiatives to advance the science and practice of psychology. The faculty is highly collaborative, frequently cooperating on research projects, co-mentoring doctoral students, and providing consultation to one another as needed. The department currently houses several prominent research laboratories that focus on research similar to the proposed study.

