1. Coach Share: If an index participant is randomized to have Coach Share ON, the coach will have continuous access to objective, real-time, detailed device data, and address data directly in all individual interactions with index participants (groups, individual weigh-ins, phone calls, texts), conveying that they are closely monitoring progress. Among index participants who are randomized to have Coach Share OFF, the coach will have no access to their device data. Index participants will be explicitly told their coach does not have data access. During groups and phone calls, the participant will self-report progress, and goal setting will be based on that self-report. Text messages from the coach will be personalized in the OFF condition, as they are when coach data sharing is ON, though these messages will not be informed by

device data. Instead, text messages will provide a reminder of key goals and strategies discussed in the previous phone call and provide encouragement for participant efforts in that area.

2. Group Share: If Group Share is ON, participants in a given LM group will view and respond to aspects of each other's self-monitoring device data in their small-group text messages. The project 'bot' will begin each text exchange by highlighting one participant's data. Over the course of 3 or 4 days, one participant's data will be highlighted each day, in order to maximize engagement. Among index participants randomized to have Group Share OFF, supportive accountability will not be the target of participant interactions and no data will be shared with LM program peers. Instead, prompts for the once monthly small group text exchanges will encourage index participants to provide social support (primarily of the informational type) to each other. Index participants will be explicitly told that they should not include information on goal progress such as weight change or minutes of PA. Similar to Group Share ON, prompts to continue the conversation will continue for several days in a row.

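### The Aim 1 model stops at the person, but Group Share is delivered in text groups nested in the tested factor, so positive text-group correlation makes its standard error too small

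*Protocol*

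**What the plan says.** Protocol, Statistical Analysis, Aim 1, sets out the model level by level. Level one is repeated weights within person. For level two, "At the second level, the individual intercept and slope will be entered as outcomes", with each sharing factor examined separately as a predictor. The test is the time-by-factor interaction, and "Both linear and higher-order time effects will be examined". Physical activity (PA) and calorie intake get similar models. No text-group or LM-group term appears.

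The protocol's opening summary has each participant exchange monthly texts "with a small group of fellow group participants". Under Group Share, the Background section has LM-group members see each other's "self-monitoring data in their small-group text messages". Under Treatment Conditions, when Group Share is ON, "participants in a given LM group will view and respond to aspects of each" other's device data, one member being featured per day: "Over the course of 3 or 4 days". When it is OFF, small-group text exchanges also run monthly, but no data go to program peers and members are told to leave out their goal progress.

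Allocation is by person. Recruitment Methods says "index participants will be randomized to treatment condition, stratifying by biological sex and baseline BMI category", and Treatment Conditions describes minimization on sex and BMI. Neither section says whether an LM group holds both ON and OFF participants. Training and Supervision balances coaches across conditions, which does not settle it.

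The power paragraph at the end of Statistical Analysis gives 238 for 80% power at 0.05 with four assessment points and a variance ratio of at least one. It calls 320 adequate with up to 25% attrition and mentions no clustering allowance.

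**The concern.** A thread in which members answer one another's data cannot also be a thread in which no data are shared and progress is not reported. One status per text group is an inference, but the delivery rules require it. Text groups are therefore nested in Group Share.

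If members of a text group change weight more alike than members of different groups, that shared part does not average out between ON and OFF at the rate a person-level model assumes. Influence between members is also what Group Share sets out to create, so zero correlation cannot be presumed.

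The LM group is a second possible source of correlation, and its direction depends on composition. If LM groups are mixed, it falls on both sides of the contrast and largely cancels. If each LM group has one status, it adds to the text-group effect.

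Group Share is one of three primary comparisons, so the validity of a primary test is at stake.

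**Working it through.** **Inputs from the protocol.** 320 participants, half ON and half OFF; five cohorts of 64; two-level model; 238 required; 25% attrition.

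**Inferred.** Text groups of m = 3 to 4, from one featured member per day over 3 or 4 days.

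**Assumed, because the protocol gives no figure.** ICC of person slopes 0.01 to 0.05 for the text group (0.005 also shown, since texting is monthly and its content differs only from month 4); LM groups of 16 (20 groups, four per cohort); fixed text-group membership; two-sided alpha; and, for power only, a slope difference of 0.40 SD.

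**The plan's own figures.** 320 × 0.75 = 240, and 240 ≥ 238, so the attrition step reproduces. The 238 cannot be derived from the protocol alone because no effect size is given. With four equally spaced points (slope sampling variance 0.2), variance ratio 1 and an assumed 0.40 SD, a noncentral F calculation returns 238 (80.1% power), and 80.4% at 240. That calculation has no cluster term.

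**Text group only.** The true-to-stated variance ratio is D = 1 + (m − 1) × ICC. Actual type I error is 2 × [1 − Φ(1.96/√D)].

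| m | ICC | D | Standard error too small by a factor of | Type I error |
|---|---|---|---|---|
| 3 | 0.005 | 1.010 | 1.005 | 5.1% |
| 3 | 0.01 | 1.02 | 1.010 | 5.2% |
| 3 | 0.05 | 1.10 | 1.049 | 6.2% |
| 4 | 0.005 | 1.015 | 1.007 | 5.2% |
| 4 | 0.01 | 1.03 | 1.015 | 5.3% |
| 4 | 0.05 | 1.15 | 1.072 | 6.8% |

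**Mixed LM groups** (m = 4, eight ON and eight OFF per LM group). D = 1 + 3 × ICC_text − ICC_LM. With the two ICCs summing to 0.05:

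- none from the LM group: D = 1.15, 6.8%
- half: 1 + 0.075 − 0.025 = 1.05, 5.6%
- three quarters: 1 + 0.0375 − 0.0375 = 1.00, 5.0%
- all: 1 − 0.05 = 0.95, 4.4%

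**One status per LM group** (m = 4). D = 1 + 3 × ICC_text + 15 × ICC_LM.

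- 0.01 + 0.01: 1 + 0.03 + 0.15 = 1.18, 7.1%
- 0.025 + 0.025: 1 + 0.075 + 0.375 = 1.45, 10.4%

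Simulation of person slopes (40,000 trials per cell, no dropout) agrees within about 0.3 percentage points.

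**Which model repairs it.** In the simulation with m = 4, for mixed LM groups at total 0.05 and for the two one-status cases above, a text-group effect alone gave 3.3% to 5.1% rejection (mixed) and 6.4% to 7.9% (one status). With both effects, in balanced ANOVA form, rejection was 4.8% to 5.2% over all 24 cells studied.

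**Power at 25% attrition** (0.40 SD, variance ratio 1, m = 4, no LM-group correlation, ICC 0.01 and 0.05).

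- Completers only, text groups kept at full size: 79.3% and 74.8%.
- Completers only, groups shrinking with dropout (D = 1 + 2.25 × ICC): 79.6% and 76.1%.
- Dropouts' earlier weights kept, visits at months 0, 3, 6, 12 and 24: 87% and 83% if all dropouts are last seen at month 12; 84% and 80% if split equally over months 3, 6 and 12; 81% and 77% if all are last seen at month 3.
- Completers only, full-size groups, larger variance ratio: 80% is kept up to ICC 0.021 at a ratio of 1.5 and 0.034 at a ratio of 2.

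**The case against.** The strongest reply concerns size. Every magnitude rests on an assumed ICC. Texting is monthly, its content differs only from month 4, and the modelled slope starts at baseline and so includes the common weekly phase. The lower ICCs are then the more plausible, and at 0.005 to 0.01 type I error is only 5.1% to 5.3%. In mixed LM groups the two-level test can even be conservative. These points stand: the text-group effect alone is modest, and too liberal a test is not guaranteed.

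A reader might infer from 240 against 238 that Group Share is underpowered. The protocol does not support that. The thin margin comes from counting completers only, at the lowest permitted variance ratio. Statistical Analysis plans likelihood-based estimation, which uses dropouts' earlier weights, and the power paragraph gives the ratio as a minimum. Either may absorb a small text-group effect.

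A reader might also infer that each LM group has one status, because Group Share ON is worded in terms of members of a given LM group. The wording leans that way, but persons are randomized and composition is not stated. The 7% to 10% figures are therefore conditional.

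It may also be said that higher levels belong in the statistical analysis plan. Degrees-of-freedom methods usually do. Here, however, the protocol itself sets out the levels of a primary model and ends them at the person.

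**Conclusion.** The structural point holds. Text groups are nested in Group Share, the stated model has no term for them, and positive slope correlation arising from the text group makes the Group Share standard error too small.

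With text groups of 3 to 4, assumed ICCs of 0.01 to 0.05 and no LM-group correlation, the nominal 5% test rejects about 5.2% to 6.8% of the time. LM-group correlation brings this to about nominal or slightly below if LM groups are mixed, and raises it to about 7% to 10% if each has one status, under ICCs of 0.01 + 0.01 to 0.025 + 0.025 and LM groups of 16. Only the sponsor can say which case applies.

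Two wider conclusions do not follow. Nothing shows that the Coach Share or Friend/Family Share tests are affected. Nor is a power shortfall established: what can be said is that the 238 carries no stated clustering allowance and has little slack on a completers-only count.

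This should be fixed, because the repair is cheap and protects a primary test. Confidence is medium, since the size depends on facts not in the protocol.

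**What to change.** - **Model.** In the Group Share Aim 1 models for weight, PA and calorie intake, add random effects of text group and of LM group on each time term tested (linear, and any higher-order term used). Use Kenward-Roger or Satterthwaite degrees of freedom and drop a component estimated at zero. Include both levels, since a text-group effect alone does not hold the error rate.
- **Records.** Record each participant's text group and LM group, and state whether LM groups mix ON and OFF.
- **Power paragraph.** Say that the 238 makes no allowance for text-group or LM-group correlation. Give Group Share power over a stated ICC range, with the effect size, text-group size and treatment of dropouts used.

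**Cost.** No extra participants and no change to delivery. With assumed LM groups of 16 and text groups of 4 (80 text groups, 20 LM groups), degrees of freedom fall from 318 to 80 − 20 − 1 = 59 if LM groups are mixed. The critical value goes from 1.967 to 2.001, so intervals are about 2% wider. With one status per LM group they fall to 20 − 2 = 18, the critical value is 2.101, and intervals are about 7% wider. The components will be imprecise. When one is truncated at zero the test is mildly conservative: simulated rejection was 4.4% to 5.3% with mixed LM groups and 3.5% to 5.0% with one status.
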